### **Change #34**

#### **Section 10:**

Frequency tables of anti-CZP antibody (ADAb) status by visit will be presented for the SS.

The number and percentage of subjects with anti-CZP antibody concentrations above 2.4 units/mL will be reported as follows:

- Number and percentage of subjects with ADAb >2.4 units/mL at the time of each visit
- Number and percentage of subjects with ADAb >2.4 units/mL at any visit during treatment (not including post treatment withdrawal or Follow-up visits)
- Number and percentage of subjects with ADAb >2.4 units/mL at any visit including post treatment withdrawal and Follow-up visits.

For the subgroup of subjects with at least 1 anti-CZP antibody level above 2.4 units/mL, the time point of occurrence of the first finding will also be displayed.

#### **Has been changed to:**

Anti-CZP antibody (ADAb) status will be determined for each visit where samples were taken. A cut point used to define ADAb negative and positive will be agreed after the sample analysis at the data evaluation meeting (DEM) prior to database lock and unblinding.

In additional, ADAb status of individual subjects will be determined and summarized using the same cut point:

- ADAb positive is defined as having a value  $>$  a defined cut point while on CZP treatment
- ADAb negative is defined as having no values  $>$  a defined cut point while on CZP treatment

The above definitions will be used for subgroup analyses by anti-CZP antibody status. Note that “while on CZP treatment” in the previous definitions refers to measurements taken when the subject is exposed to CZP study treatment. Measurements at Baseline, at the Follow-up, and at any visit  $>70$  days after last CZP dose are not included in this algorithm.

Note that for purposes of classifying a subject as negative or positive for anti-CZP antibodies, the value must be above the defined cut point and must occur after the subject has had at least one injection of CZP. By definition, a subject cannot be positive for anti-CZP antibodies if they have only received PBO, regardless of how high the value may be. However, a subject randomized to PBO and escaping to CZP may become positive based on values during the OL period while receiving CZP.

A frequency table of anti-CZP antibody status by visit will be presented. In addition, the first occurrence of anti-CZP antibody positive will be tabulated by visit including the cumulative count. That is, each anti-CZP antibody positive subject will be counted only once at the visit where anti-CZP antibody positivity was first observed. The table will also include a summary of the total number of anti-CZP antibody and the total number of positive results observed on treatment (at any visit during treatment not including post treatment withdrawal or Follow-up visits) and at any visit including post treatment withdrawal and Follow-up visits.

### **Change #35**

#### **Section 11.1:**

Exposure to the open-label CZP treatment will also be calculated using the above 4 methods considering only dosing during the time the patient is receiving open-label CZP study medication. Exposure to open-label other treatments will not be calculated.

For the first 3 approaches, tables will summarize exposure days for the placebo, CZP 200mg Q2W and open-label CZP treatment groups.

#### **Has been changed to:**

Exposure to the open-label CZP treatment will also be calculated using the above 4 methods considering only dosing during the time the subject is receiving open-label CZP study medication prior to Week 52 visit. Exposure during the SFE period will be calculated using methods 2, 3 and 4 assuming first dose in the SFE period starts when the subject takes their loading dose/first dose of open-label CZP in the SFE period and ends when the subject has their last administration of study medication (or if missing, the date of withdrawal). Total CZP exposure will be calculated using all 4 methods, by summing the exposure to CZP during the double-blind, open-label CZP and SFE periods. Note that for method 1, the SFE period will be

excluded from the Total CZP as data is not collected on dose administration. Exposure to open-label other treatments will not be calculated.

For the first 3 approaches, tables will summarize exposure for the placebo, CZP 200mg Q2W, open-label CZP treatment groups (split by the treatment taken during the double-blind period), SFE open-label CZP and Total CZP.

**Change #36**

**Section 11.2**

AE start dates will be examined to determine if they are treatment-emergent and attributable to the double-blind treatment period or open-label period. AEs occurring either before double-blind study drug administration (pre-treatment) or outside of the windows described below will be defined as non-treatment emergent.

Table 11-1: Assignment of Adverse Events to Study Periods		
Type of Subject	Assignment Rule Based on AE Start Date	Assignment
Subjects who participate only in the double-blind period	Start date is on or after first study drug administration during the double-blind period and before the last study drug administration + 70 days.	Double-blind treatment-emergent
Subjects who enter the open-label period prior to Week 52	1. Start date is on or after first study drug administration during the double-blind period and before the start date of open-label CZP or other treatment.	Double-blind treatment-emergent
	2. Start date is on or after the start date of open-label CZP and before the start date of open-label other treatment.	Open-label CZP
	3. Start date is on or after the start date of open-label other treatment.	Open-label other treatment

If AE intensity or relationship is missing, then the given event will be imputed as severe or related, respectively.

The frequency of all AEs including TEAEs will be presented for each treatment group separately by System Organ Class, high level term, and preferred term. The data will be displayed as number of subjects experiencing the AEs, percentage of subjects, and number of AEs. Certain summaries will also include exposure-adjusted incidence rates and event rates. Only TEAEs occurring in the double-blind period and open-label period will be presented.

The following AE summaries will be presented:

- Overview of TEAE
- TEAE

- Serious TEAE
- Non-serious TEAE
- TEAE with fatal outcome
- TEAE leading to permanent withdrawal of study medication
- Severe TEAE (included in TEAE table by intensity)
- Drug-related TEAE (included in TEAE table by relationship)
- Serious TEAE by relationship
- Non-serious TEAE by relationship
- Fatal TEAE by relationship
- Injection reactions (Injection site reactions, systemic injection reactions, acute systemic injection reactions, and delayed systemic injection reactions)
- TEAE of special interest (see below)
- TEAE sorted by incidence of PTs in the CZP 200mg group (SOC and HLT will not be utilized)
- Non-serious TEAE with an incidence of at least 5% in 1 of the 2 randomized groups (HLT will not be utilized)
- Non-serious TEAE with an incidence of at least 5% in 1 of the 2 randomized groups by relationship (HLT will not be utilized)
- TEAE subject numbers

The AEs of interest and the approach for summarizing them are described below:

3. Serious infections, including opportunistic infections. Serious infections will be summarized using the Serious TEAE table. No separate table is planned. In addition, opportunistic infections (including tuberculosis) will be presented in a table using UCB-defined search criteria.
4. Malignancies, including lymphoma. These will be presented in 2 tables using the criteria SMQ = "Malignant or unspecified tumours" and SMQ="Malignancies", respectively.
5. Congestive heart failure. These will be manually identified by the study physician from the TEAE table. No separate table is planned. In addition, major adverse cardiac events (MACE) will be presented in a table using UCB-defined search criteria and will include fatal and serious non-fatal myocardial infarction, cerebrovascular events and congestive heart failure.
6. Demyelinating-like disorders. These will be manually identified by the study physician from the previously described TEAE table. No separate table is planned.
7. Aplastic anemia, pancytopenia, thrombocytopenia, neutropenia, and leucopenia. These will be presented in a table using the criteria SMQ = "Haematopoietic cytopenias" in the subset of SAEs.

8. Serious bleeding events. These will be presented in a table using the criteria SMQ = “Haemorrhages” in the subset of SAEs.
9. Lupus and lupus-like illness. These will be manually identified by the study physician from the TEAE table. No separate table is planned.
10. Serious skin reactions (eg, Stevens-Johnson Syndrome, toxic epidermal necrosis, and erythema multiforme). These will be manually identified by the study physician from Serious TEAE table. No separate table is planned.

The tables for 1, 2, 3, 5, and 6 above will include the incidence rate with associated 95% CI, and the exposure adjusted event rate.

Although not an AE of interest, hepatic events will also be summarized. They should be identified using the following 5 SMQs: Cholestasis and jaundice of hepatic origin; Hepatic failure, fibrosis, and cirrhosis and other liver damage-related conditions; Hepatitis, noninfectious; Liver-related investigations, signs and symptoms; and Liver-related coagulation and bleeding disturbances.

Because subjects will be able to adjust background medications during the study, some additional AE tables will be prepared in which events occurring while on certain background medications will be summarized. The list of these supportive tables is as follows:

- TEAEs reported after starting a new biologic, but within 10 weeks of stopping CZP
- TEAEs reported one month after changing NSAID type
- TEAEs reported three months after changing or adding a DMARD
- TEAEs reported within one month of an addition of oral corticosteroids or 50% increase in dose

The purpose of these tables will be to assess whether any observed treatment differences in the AE profile may be due, in part, to these prespecified background medications.

A TEAE table will also be presented for the ‘anti-CZP antibody status’ subgroup. Only the subjects exposed to CZP in the double-blind period will be considered and the double-blind TEAEs will be displayed by the antibody status (negative, positive as defined in section 10). A further positive column will be presented by summarizing the TEAEs occurring after the onset of the positive antibody status. The incidence rate will be presented in addition to the associated 95% CI, and the exposure adjusted event rate.

The TEAE incidence rates will also be adjusted for exposure (as calculated using methods 3 and 4 in [Section 11.1](#)) and reported by 100 patient-exposure years. Two approaches will be applied to adjust for exposure. One will only use the first occurrence of an AE with corresponding exposure (exposure-adjusted incidence rate [EAIR]) and the second approach will use all AEs and the entire exposure (exposure-adjusted event rate [EAER]).

For the EAIR, the first occurrence of an TEAEs for a certain treatment group will be utilized (either placebo or CZP 200mg Q2W for the double-blind period or open-label CZP) and divided by the sum of exposure of all subjects in the respective treatment group, where subjects experiencing the respective AE will be censored at the time of occurrence of the AE. The EAIR will be multiplied by a factor of 100 to give a rate per 100 patient-years.

For the EAER, all TEAEs for a certain treatment group will be utilized (either placebo or CZP 200mg Q2W for the double-blind period or open-label CZP) and divided by the sum of exposure of all subjects in the respective treatment group. The EAER will be multiplied by a factor of 100 to give a rate per 100 patient-years.

The summary of TEAEs, serious TEAEs, and TEAEs leading to permanent withdrawal of study medication will include the EAIR (with corresponding 95% exact CI) and EAER. The confidence interval for the EAIR will be based on Poisson rate CIs. The bounds of the exact 95% CIs are estimated by

$$\text{lower bound} = \frac{1}{2 \cdot t} \cdot \chi^2_{2 \cdot (\text{number of patients with events}), 0.025} \quad \text{and} \quad \text{upper bound} = \frac{1}{2 \cdot t} \cdot \chi^2_{2 \cdot (\text{number of patients with events} + 1), 0.975}$$

$\chi^2_{n,\gamma}$  denotes the chi-distribution with n degrees of freedom and quantile  $\gamma$  and t is the exposure censored at the time of occurrence of the AE.

**Has been changed to:**

AE start dates will be examined to determine if they are treatment-emergent and attributable to the double-blind period, open-label period or SFE period. AEs occurring either before double-blind study drug administration (pre-treatment) or outside of the windows described below will be defined as non-treatment emergent.

**Table 11-1: Assignment of Adverse Events to Study Periods**

Type of Subject	Assignment Rule Based on AE Start Date	Assignment
Subjects who do not enter the open-label period prior to Week 52 and do not enter SFE	Start date is on or after first study drug administration during the double-blind period and on or before the last study drug administration in the double-blind period + 70 days.	Double-blind TEAE
Subjects who do not enter the open-label period prior to Week 52 but do enter SFE after Week 52	Start date is on or after first study drug administration during the double-blind period and prior to loading dose/first dose administration in SFE	Double-blind TEAE
Subjects who enter the open-label period prior to Week 52	1. Start date is on or after first study drug administration during the double-blind period and before the start date of open-label CZP or other treatment.	Double-blind TEAE

Table 11-1: Assignment of Adverse Events to Study Periods		
Type of Subject	Assignment Rule Based on AE Start Date	Assignment
	2. Start date is on or after the start date of open-label CZP and either before the start date of open-label other treatment (for subjects moving into open-label other treatment), or before the loading dose/first dose administration in SFE (for subjects moving into SFE period) or before the last study drug administration during the Open-label CZP period (prior to Week 52) + 70 days (for subjects who complete the Follow-up visit not entering SFE).	Open-label CZP TEAE
	3. Start date is on or after the start date of open-label other treatment.	Open-label other treatment TEAE
Subjects who enter the open-label SFE period (Week 52 completers only)	Start date is on or after the loading dose/first dose administration in SFE.	SFE TEAE

If AE intensity or relationship is missing, then the given event will be imputed as severe or related, respectively.

The frequency of all AEs including TEAEs will be presented for each treatment group separately by System Organ Class, high level term, and preferred term. The data will be displayed as number of subjects experiencing the AEs, percentage of subjects, and number of AEs. Certain summaries will also include exposure-adjusted incidence rates and event rates. TEAEs will be summarized by treatment and period as described in [Section 3.6](#).

The following AE summaries will be presented:

- Overview of TEAE
- TEAE
- Serious TEAE
- Non-serious TEAE
- TEAE with fatal outcome
- TEAE leading to permanent withdrawal of study medication
- Severe TEAE (included in TEAE table by intensity)
- Drug-related TEAE (included in TEAE table by relationship)
- Serious TEAE by relationship

- Non-serious TEAE by relationship
- Fatal TEAE by relationship
- Injection reactions (Injection site reactions, systemic injection reactions, acute systemic injection reactions, and delayed systemic injection reactions)
- TEAE of special interest (see below)
- TEAE sorted by incidence of PTs in the CZP 200mg group (SOC and higher level term [HLT] will not be utilized)
- Non-serious TEAE with an incidence of at least 5% in 1 of the 2 randomized groups (HLT will not be utilized)
- Non-serious TEAE with an incidence of at least 5% in 1 of the 2 randomized groups by relationship (HLT will not be utilized)
- TEAE subject numbers

The AEs of interest and the approach for summarizing them is briefly described below. Further information is provided in the guidance document (AEs of Interest – Cimzia Program 9February2017).

11. Serious infections, including opportunistic infections. Serious infections will be summarized using the Serious TEAE table. No separate table is planned. In addition, opportunistic infections (including tuberculosis) will be presented in a table using UCB-defined search criteria.
12. Malignancies, including lymphoma. These will be presented in 2 tables using the Standardized MedDRA Query (SMQ) criteria “Malignant or unspecified tumours” and “Malignant tumours” respectively.
13. Serious cardiovascular events. These will be presented in a table including all serious TEAEs with the SMQs of “Haemorrhagic central nervous system vascular conditions” and “Ischaemic central nervous system vascular conditions”, including all serious TEAEs with the HLT of “Ischaemic coronary artery disorders” except events coding to PTs of “Chest Pain” or “Chest discomfort” and including all serious TEAEs with HLTs of “Heart Failures NEC”, “Left Ventricular Failures”, or “Right Ventricular Failures” and which also code to the SOC of “Cardiac Disorders”.
14. Congestive heart failure. These will be manually identified by the study physician from the TEAE table. No separate table is planned.
15. Demyelinating-like disorders. These will be manually identified by the study physician from the previously described TEAE table. No separate table is planned.
16. Aplastic anemia, pancytopenia, thrombocytopenia, neutropenia, and leucopenia. These will be presented in a table using the criteria SMQ = “Haematopoietic cytopenias” in the subset of Serious TEAEs.
17. Serious bleeding events. These will be presented in a table using the criteria SMQ = “Haemorrhage terms (excl laboratory terms)” in the subset of Serious TEAEs.

18. Lupus and lupus-like illness. These will be manually identified by the study physician from the TEAE table. No separate table is planned.

19. Serious skin reactions (eg, Stevens-Johnson Syndrome, toxic epidermal necrosis, and erythema multiforme). These will be manually identified by the study physician from Serious TEAE table. No separate table is planned.

The tables for 1, 2, 3, 5, and 6 above, will include the exposure-adjusted incidence rate (EAIR) with associated 95% CI, and the exposure-adjusted event rate (EAER) as described below.

Although not officially AEs of interest, the following events will also be summarized as described in the AEs of Interest – Cimzia Program 9 February 2017 guidance document.

20. Hepatic events. These will consist of a subset of all TEAEs, identified using the following 5 SMQs: Cholestasis and jaundice of hepatic origin; Hepatic failure, fibrosis, and cirrhosis and other liver damage-related conditions; Hepatitis, noninfectious; Liver-related investigations, signs and symptoms; and Liver-related coagulation and bleeding disturbances.

21. Hypersensitivity reactions and anaphylactic reactions. Hypersensitivity reactions will be summarized as any TEAEs occurring on the same day or the day after injection was received, which code to the following preferred terms: Administration site hypersensitivity, Documented hypersensitivity to administered product, Drug hypersensitivity, Hypersensitivity, Hypersensitivity vasculitis, Infusion site hypersensitivity, Injection site hypersensitivity, Medical device site, hypersensitivity, Type II hypersensitivity or Type IV hypersensitivity reaction. Anaphylactic reactions will be defined using an algorithmic approach as described in the “AEs of Interest – Cimzia Program 9 February 2017” guidance document.

Because subjects will be able to adjust background medications during the study, some additional AE tables will be prepared in which events occurring while on certain background medications will be summarized. The list of these supportive tables is as follows:

- TEAEs reported after starting a new biologic, but within 10 weeks of stopping CZP
- TEAEs reported one month after changing NSAID type
- TEAEs reported three months after changing or adding a DMARD
- TEAEs reported within one month of an addition of oral corticosteroids or 50% increase in dose

The purpose of these tables will be to assess whether any observed treatment differences in the AE profile may be due, in part, to these prespecified background medications.

A TEAE table will also be presented for the ‘anti-CZP antibody status’ subgroup defined in [Section 10](#). Only subjects exposed to CZP and only TEAEs occurring after first dose of CZP will be considered. A further column will be presented summarizing TEAEs occurring after the onset of the positive antibody status. The EAIR will be presented in addition to the associated 95% CI, and the EAER.

The TEAE incidence rates will also be adjusted for exposure (as calculated using methods 3 and 4 in [Section 11.1](#)) and reported by 100 subject years of exposure. 100 subject-years is defined as the sum of the exposure / number of subjects \*100. Two approaches will be applied to adjust

for exposure. One will only use the first occurrence of an AE with corresponding exposure (EAIR) and the second approach will use all AEs and the entire exposure (EAER).

For the EAIR, the first occurrence of an TEAEs for a certain treatment group will be utilized (either placebo or CZP 200mg Q2W for the double-blind period or open-label CZP) and divided by the sum of exposure of all subjects in the respective treatment group, where subjects experiencing the respective AE will be censored at the time of occurrence of the AE. The EAIR will be multiplied by a factor of 100 to give a rate per 100 subject-years.

For the EAER, all TEAEs for a certain treatment group will be utilized (either placebo or CZP 200mg Q2W for the double-blind period or open-label CZP) and divided by the sum of exposure of all subjects in the respective treatment group. The EAER will be multiplied by a factor of 100 to give a rate per 100 subject-years.

The summary of TEAEs, serious TEAEs, and TEAEs leading to permanent withdrawal of study medication will include the EAIR (with corresponding 95% exact CI) and EAER. The confidence interval for the EAIR will be based on Poisson rate CIs. The bounds of the exact 95% CIs are estimated by

$$\text{lower bound} = \frac{1}{2 \cdot t} \cdot \chi^2_{2, \text{number of patients with events}, 0.025} \quad \text{and} \quad \text{upper bound} = \frac{1}{2 \cdot t} \cdot \chi^2_{2, (\text{number of patients with events} + 1), 0.975}$$

$\chi^2_{n, \gamma}$  denotes the chi-distribution with n degrees of freedom and quantile  $\gamma$  and t is the exposure censored at the time of occurrence of the AE.

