5. Demyelinating-like disorders will be presented in table which is based on the SMQ = “Demyelination”. The SMQ search should include all TEAEs which code to a PT included in Scope=Narrow group within the SMQ. TEAEs which code to a PT included in the Scope=Broad group within the SMQ should be excluded from the search.
6. Aplastic anemia, pancytopenia, thrombocytopenia, neutropenia, and leucopenia. These will be presented in a table using the criteria SMQ = “Haematopoietic cytopenias” in the subset of Serious TEAEs.
7. Serious bleeding events. These will be presented in a table using the criteria SMQ = “Haemorrhage terms (excl laboratory terms)” in the subset of Serious TEAEs.
8. Lupus and lupus-like illness. These will be manually identified by the study physician from the TEAE table. No separate table is planned.
9. Serious skin reactions (eg, Stevens-Johnson Syndrome, toxic epidermal necrosis, and erythema multiforme). These will be manually identified by the study physician from Serious TEAE table. No separate table is planned.

The tables for 1, 2, 3, 5, and 6 above, will include the exposure-adjusted incidence rate (EAIR) with associated 95% CI, and the exposure-adjusted event rate (EAER) as described below.

Although not officially AEs of interest, the following events will also be summarized as described in the AEs of Interest – Cimzia Program 2018-01-05 guidance document.

1. Hepatic events. These will consist of a subset of all TEAEs, identified using the following 5 SMQs: Cholestasis and jaundice of hepatic origin; Hepatic failure, fibrosis, and cirrhosis and other liver damage-related conditions; Hepatitis, noninfectious; Liver-related investigations, signs and symptoms; and Liver-related coagulation and bleeding disturbances.
2. Hypersensitivity reactions and anaphylactic reactions. Hypersensitivity reactions will be summarized as any TEAEs occurring on the same day or the day after injection was received, which code to the following preferred terms: Administration site hypersensitivity, Documented hypersensitivity to administered product, Drug hypersensitivity, Hypersensitivity, Hypersensitivity vasculitis, Infusion site hypersensitivity, Injection site hypersensitivity, Medical device site, hypersensitivity, Type II hypersensitivity or Type IV hypersensitivity reaction. Anaphylactic reactions will be defined using an algorithmic approach as described in the “AEs of Interest – Cimzia Program 2018-01-05” guidance document.

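### Serious bleeding is the only adverse event of special interest with its own table but no exposure-adjusted rate or confidence interval assigned to it

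*SAP*

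**What the plan says.** Section 11.2 of the SAP sets out the special-interest list. Separate tables are planned for opportunistic infections (item 1), malignancies (2), serious cardiovascular events (3), demyelinating-like disorders ("5. Demyelinating-like disorders will be presented in table which is based on the SMQ"), cytopenias (6) and serious bleeding ("7. Serious bleeding events. These will be presented in a table using the criteria SMQ"). Heart failure (4), lupus (8) and serious skin reactions (9) are identified by physician review, without a table of their own.

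The rates are then assigned by number: "The tables for 1, 2, 3, 5, and 6 above, will include the exposure-adjusted incidence rate (EAIR) with associated 95% CI", plus the EAER. Item 7 is not in that list.

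The same section says that AE tables in general show subjects, percentages and numbers of events, and that only certain summaries add exposure-adjusted rates. The overall summaries of TEAEs, serious TEAEs and TEAEs leading to withdrawal of study medication do carry EAIR with an exact interval and EAER. Section 3.6 lists the AE columns. They include double-blind placebo, double-blind CZP, and a total CZP column pooling the double-blind, open-label and SFE periods.

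**The concern.** Serious bleeding is a named adverse event of special interest in Section 2.2.4.1.1. Its table is built in the same way as the cytopenia table: an SMQ applied to serious TEAEs. The cytopenia table gets an EAIR, an interval and an EAER; the bleeding table does not, and the SAP gives no reason.

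Crude percentages rise with length of observation. Where columns of very different duration stand side by side, a table without rates invites the reader to take longer follow-up for higher risk. For the grouped bleeding risk there would also be no interval showing how little can be concluded from few events.

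**Working it through.** **Step 1. Map the number list onto the items.** The current text is the operative one. The amendment log (Section 14.2, Change #36) serves only to show where the list came from. Its printed numbers run on, so items are counted by position. In the list before Amendment 2 the first item is printed as "3. Serious infections, including opportunistic infections", and bleeding as "8. Serious bleeding events. These will be presented in a table using the criteria SMQ", so bleeding is at position 8 − 2 = 6. In the Amendment 2 list, printed 11 to 19, bleeding is printed 17, so its position is 17 − 10 = 7.

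| Position | Before Amendment 2 | Amendment 2 | Current Section 11.2 |
|---|---|---|---|
| 1 | infections, table | infections, table | infections, table |
| 2 | malignancies, table | malignancies, table | malignancies, table |
| 3 | heart failure with MACE, table | serious cardiovascular, table | serious cardiovascular, table |
| 4 | demyelination, none | heart failure, none | heart failure, none |
| 5 | cytopenias, table | demyelination, none | demyelination, table |
| 6 | serious bleeding, table | cytopenias, table | cytopenias, table |
| 7 | lupus, none | serious bleeding, table | serious bleeding, table |
| 8 | skin, none | lupus, none | lupus, none |
| 9 | – | skin, none | skin, none |

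Compare the items with a table with the rate list {1, 2, 3, 5, 6}:

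- Before Amendment 2 ("The tables for 1, 2, 3, 5, and 6 above will include the incidence rate with associated 95% CI"): tables {1, 2, 3, 5, 6}. Exact match, bleeding included.
- Amendment 2: tables {1, 2, 3, 6, 7}. Bleeding has a table and no rate. Demyelination is assigned a rate, although of it the text says "These will be manually identified by the study physician from the previously described TEAE table. No separate table is planned".
- Current: tables {1, 2, 3, 5, 6, 7}. The only table without a rate is item 7.

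Amendments 2 and 3 each say that all modifications are detailed. Amendment 3, Change #4, records updates to the cardiovascular and demyelinating items. Neither amendment records a decision to drop rates for bleeding.

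**Step 2. Can the grouped rate be recovered from other tables?** The serious TEAE summary gives rates by SOC, HLT and preferred term. None of those rows is the haemorrhage SMQ. Section 11.1, method 4, censors exposure at first occurrence, separately for each preferred term. Adding rows would count a subject with two bleeding terms twice and would mix different denominators. The grouped EAIR and its interval therefore cannot be built from those rows. The grouped EAER can be approximated by dividing tabulated events by tabulated exposure.

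**Step 3. How far do the columns differ in follow-up?** Inputs: maximum double-blind duration 350 days (Section 7); exposure extends 70 days past the last injection (Section 11.1, method 3); last SFE dosing visit at Week 154 (Section 2.3.1), which is 154 × 7 = 1078 days.

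- Randomized arm, planned maximum: 350 + 70 = 420 days = 1.15 years.
- Pooled CZP including SFE, planned maximum: 1078 + 70 = 1148 days = 3.14 years, assuming continuous dosing and a single 70-day tail.
- Ratio: 1148 / 420 = 2.73.

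With a constant true rate *r* in every column, the crude percentage is 1 − exp(−*r* × years). The SAP gives no bleeding rate, so *r* is an assumption:

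| Assumed rate per 100 subject-years | 420 days | 1148 days | Ratio |
|---|---|---|---|
| 0.2 | 0.230% | 0.627% | 2.73 |
| 0.5 | 0.573% | 1.559% | 2.72 |
| 1.0 | 1.143% | 3.094% | 2.71 |
| 2.0 | 2.274% | 6.093% | 2.68 |

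**Step 4. The randomized comparison.** Planned duration is the same in both arms, so the ratio is 1.0 by design. If mean placebo follow-up were 80%, 60% or 50% of that on CZP because of earlier switching (an assumption, at 1 per 100 subject-years), the crude ratio at equal rates would be 1.25, 1.66 or 1.99. The SAP gives no figure for the size of any such difference.

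**The case against.** The current text does not contradict itself. Each of the five numbers points to an item with a table, and the section says that only certain summaries carry rates. The hepatic and hypersensitivity summaries are not assigned rates there either. Further detail is left to a sponsor guidance document that is not at hand, so a deliberate omission cannot be excluded. This stands: the stale numbering is an inference. It is a strong one, because under Amendment 2 the same sentence promised a rate for a table that did not exist. That mismatch is in superseded text only and is no error in the current plan.

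A reader might infer that serious bleeding is compared only as crude percentages. The documents do not support that. Event counts are shown, every event in the bleeding table is also a serious TEAE and so appears in a summary with rates, and serious haemorrhagic central nervous system events also fall in the item 3 table, which has rates. What is missing is the rate and interval for the SMQ group.

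A reader might also infer that follow-up is very unequal between the randomized arms. The SAP plans equal durations. Investigators may stop study treatment in non-responders, so earlier placebo exit is plausible, but its size is not given. The inequality by design lies between placebo and the pooled, non-randomized CZP columns.

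Lastly, events will be few. At an assumed 0.5 per 100 subject-years, 150 placebo subjects at maximum exposure give 150 × 0.573% ≈ 0.9 subjects with an event, so any interval will be wide. That is true, but the SAP still attaches rates to cytopenias, which are built in the same way, and a wide interval tells the reader how little the data can show.

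**Conclusion.** The point holds in a limited form. In the current Section 11.2, serious bleeding is the one tabulated special-interest event without an EAIR, its 95% interval and an EAER. The likely cause is a number list not updated when Amendment 2 inserted an item; the log supports this but does not prove it.

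The consequence is confined to safety reporting. Read against placebo, the pooled CZP column including the SFE would show a crude bleeding percentage up to about 2.7 times as high with no true difference in rate. That figure assumes a constant, equal rate (0.2 to 2 per 100 subject-years was tried) and both columns at their planned maximum. Actual mean exposures are not in the SAP and would move it. Between the randomized arms no distortion follows from the design. No efficacy conclusion is affected. The correction is worth making because it restores a rate for a named safety risk at very little cost.

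**What to change.** In Section 11.2, replace the number list by the names of the tables: opportunistic infections, malignancies, serious cardiovascular events, demyelinating-like disorders, cytopenias and serious bleeding (items 1, 2, 3, 5, 6 and 7). State that each carries the EAIR with 95% CI and the EAER. Naming them keeps the sentence correct if the list is reordered again. If the omission was intended, say so and give the reason.

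The cost is one sentence in the SAP and the rate columns in one existing table. The rate and interval methods are already specified in Sections 11.1 and 11.2, and the same grouped calculation is already needed for the cytopenia table.
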